THE EFFECT OF THERAPEUTIC TOUCH AND MUSIC REST ON SLEEPING APPLIED TO CHILDREN WITH LIVER TRANSPLANTATION

ID: TDK-2020-2358

NCT ID not yet assigned

Initial Release: 09/09/2021

MATERIAL AND METHOD

Desing of Research

The research was planned as a quasi-experimental study.

Place and Time of Research

The research will be carried out at İnönü University Turgut Özal Medical Center Liver Institute Pediatrics Clinic between February 2021 and October 2021. Pediatric transplant patients are followed in the 19-bed pediatric clinic of the institute.

Population and Sample of the Research

The population of the research will be children between the ages of 0-18 who had liver transplantation at İnönü University Turgut Özal Medical Center Liver Institute between February 2021 and October 2021 and were hospitalized in the pediatric clinic of the institute. The number of patients to be included in the study was calculated as 50 when the calculation was made by taking the confidence interval of 95% in the sample whose population is known. Of the 50 patients sampled, 24 will be included in therapeutic touch groups and 24 in music concert groups.

Randomization:

Assignment of the participants to the control and experimental groups will be done by stratification and block randomization method. Children will be stratified according to their age (0-1, 2-5, 6-12, 13-18 years) and randomization with blocks will be made. In order to prevent bias, children who were stratified were assigned to the control and experimental groups by drawing lots. The research groups will be written on separate papers and the group will be

determined by drawing lots during data collection. In this way, the number of children included in the groups and the probability of each child to be included in the study in the experimental or control group will be equalized.

Inclusion criteria:

*Being within a period of at least one month and at most two years after the transplant

* 0-18 years old

* Conscious

*spontaneous breathing

*No hearing problems

*Pain free

*Children who do not use sleeping pills will be included in the study.

Data Collection Tools

The data will be collected by face-to-face interview technique with the "Introductory Information Form", "Actigraphy" created by the researcher between February 2021 and October 2021.

Introductory Information Form

The "Introductory Information Form", prepared by the researcher in line with the literature, consists of a total of 15 questions such as the age, gender, education status of the child and parent, and the time of transfer.

Actigraphy

Actigraphy measures the sleep and wake cycles of children and adolescents, detects motor activities with precision, is worn on wrists or ankles, and allows for recording and storing resting and activity patterns in a digital environment; small, lightweight, portable device in the form of a watch (Ertan & Alkan, 2012). The actigraphy device, which can be easily attached to the wrist of the patients, is used to evaluate and document the physical movements of the patients related to sleep. The device can keep a record of the patient's activity for 24 hours. The patient's information can be read and evaluated with the help of a special software of the device.

Data Collection

Data will be collected through face-to-face interviews with children aged 0-18 years, who had liver transplantation at İnönü University Turgut Özal Medical Center Liver Institute and were hospitalized in the pediatric clinic of the institute. The study will consist of therapeutic touch group and music groups. Which group the participants will be in will be determined by drawing lots. One of the experimental groups will be treated with therapeutic touch, and the other will be listened to a music preferred by the family/child. In both groups, children's sleep will be evaluated with pre-test, post-test and follow-up applications. In this study, applications to the "Therapeutic touch" and "music" groups will be done once a day (morning or afternoon) for three days, in the form of a 15-20 minute application period. Children's sleep will be evaluated with "Actigraphy" the day before the application, the day the application ends, and the fourth day after the application.

Intervention Materials

Therapeutic Touch:

Therapeutic touch; It is a low-cost, non-contra-indications, easy-to-apply and non-invasive form of complementary therapy that can be applied anywhere and at any time (Vanaki et al., 2016). Therapeutic touch was developed by Krieger in 1975 as a nursing intervention to help and even heal the patient by balancing the patient's energy field (Marta et al., 2010). The basic assumption of therapeutic touch is that people have energy fields and these energy fields interact with the environment (Hanley, 2008). Therapeutic touch aims to harmonize, renew and heal the flow of the human energy field by removing the blockages of a person's biofield (Mueller et al., 2019). Unlike other touch-based methods such as massage therapy, therapeutic touch does not require the practitioner to physically touch the patient. Instead, the practitioner uses their hands to focus their energy and intent to help the recipient (Hanley, 2008).

In order to practice therapeutic touch, the researcher attended a certified course organized by the "Therapeutic Touch Association" and received a post-course certificate.

Music Rest:

The use of music in the treatment of diseases has been seen in many civilizations since ancient times. In ancient Greek and Roman communities, individuals resorted to music to get rid of their humanitarian problems, while in Ancient Egypt, music was used to give strength to patients during birth (Kor & Adar, 2016). In today's studies, it has been determined that music positively affects the physiological parameters, nutrition, hospital stay and sleep of the patients (O'Toole et al., 2017; Van Der Heijden et al., 2016). It is important that the sound level is within

the appropriate limits while listening to music to the patients. The American Academy of Pediatrics recommends a sound level between 45dB- a maximum of 65dB (ACOG - AAP, 2012). The World Health Organization recommends a sound level of 35 dB during the day and 30 dB at night (Berglund et al., 2000). In this study, a music (such as lullaby, classical music) preferred by the patient or his family will be played to the children for 20 minutes once a day (morning or afternoon) for three days to help the child sleep. The sound level of the music played will be kept between 45-65 dB.

Nursing Initiative

In this study, the effects of "Therapeutic Touch" and "Music Concert", which are nursing practices, on the sleep of children who have been transferred will be compared.

Therapeutic Touch Group:

*Parents and children will be informed about "Therapeutic Touch", which is an easy-to-apply and non-invasive application before the procedure.

*One day before starting the "Therapeutic Touch" application, the child's sleep will be evaluated with "Actigraphy". Starting the day after the first measurement, "Therapeutic Touch" will be done in the form of a 20-minute daily application period for three days.

* Before the "Therapeutic Touch" application, the patient's room will be ventilated and a spacious and quiet environment will be provided during the application.

TD process:

*After the procedure was explained, the focus was on the child to be treated,

*Intended to help the child's treatment and sleep,

*The patient's energy field was scanned with the hands at a distance of 8-12 cm from the patient's skin (2 times)

*To remove the blockages determined regarding the energy flow and to facilitate the energy flow, manual cleaning was performed (2 times),

*Imbalances in the energy fields were tried to be treated by using mental visualization techniques such as dreaming, positive thinking and visualization, by directing the universal life energy to sick individuals with calm and rhythmic hand movements (2 times),

*Reassessed to determine whether success has been achieved in treating imbalances in the energy field.

Music Rest Group:

*Parents and children will be informed about the “Music Rest” before the procedure.

*One day before the “Music Rest” practice, the child's sleep will be evaluated with “Actigraphy”. Starting the day after the first measurement, the “Music Rest” will be held for three days as a 20-minute practice period per day. In order to help the child sleep, the child will be listened to music (such as lullaby, classical music) preferred by the patient or his family.

*Before the “Music Rest” application, the patient's room will be ventilated and a spacious and quiet environment will be provided during the application.

*The sound level of the music played will be kept between 45-65 dB.

*Nursing interventions will be written in more detail after the data of the research is collected.

Variables of the Study

Dependent variables: “Actigraphy”

Independent variables: Therapeutic touch, recital

Control variable: Age, gender, height, weight, place of residence, economic status, pain

Evaluation of Research Data

IBM SPSS Statistics 25.0 package program will be used in the evaluation of the research data. Percentage, mean, standard deviation, normal distribution, t-test in independent groups, t-test and ANOVA tests in dependent groups, multiple linear regression and correlation analyzes will be used in the evaluation of the data. Statistical significance level will be accepted as $p<0.05$.

Ethical Principles of Research

Before the study, children and their parents will be included in the study after an explanation is given about the study and their written and verbal consents are obtained. Ethics committee approval was obtained from İnönü University Clinical Research Ethics Committee and institutional permission was obtained from İnönü University Turgut Özal Medical Center Liver Institute. It will be explained to the parents that not participating in the study will not have a negative effect on the treatment of their children.

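### Does the population sentence confine the trial to transplants done in February–October 2021, leaving the two-year inclusion limit without effect?

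*Protocol*

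**What the plan says.** Under Population and Sample of the Research, the Protocol takes as its population children aged 0–18 who were transplanted at the "Liver Institute between February 2021 and October 2021 and were hospitalized in the pediatric clinic of the institute".

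The Inclusion criteria ask for "Being within a period of at least one month and at most two years after the transplant".

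The same months appear twice more. Place and Time of Research says that the study will run at the "Liver Institute Pediatrics Clinic between February 2021 and October 2021". Data Collection Tools says that data will be gathered with instruments "created by the researcher between February 2021 and October 2021", where the dates can only sensibly mean the collection period.

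Under Data Collection, the children are described again, without dates, as transplanted at the "Liver Institute and were hospitalized in the pediatric clinic of the institute". The Introductory Information Form covers "education status of the child and parent, and the time of transfer". The Protocol also calls these children transferred under Nursing Initiative, so this item is apparently the time of transplant.

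**The concern.** In the population sentence the dates follow the transplant and come before the separate clause on hospitalisation. Read as written, they date the operation. Transplant and measurement then share one nine-month window, with three consequences:

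- The two-year upper limit can never apply.
- The one-month minimum leaves no eligible child in the opening weeks of data collection.
- A child transplanted in, say, 2020 and in hospital during the study meets the inclusion criterion but falls outside the stated population.

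At stake is to whom the result applies: children 1 to about 9 months after transplant, or 1 to 24 months. The sample size is also said to rest on a population of known size, which presupposes one definition of that population.

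**Working it through.** **Inputs.** The months February and October 2021 (Population and Sample; Place and Time; Data Collection Tools), the one-month and two-year limits (Inclusion criteria), and the measurement schedule (Data Collection). The documents give months only, so every day of the month below is an assumption. A month is taken as 30.4375 days.

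**1. Longest time since transplant if the dates belong to the transplant.**
- Widest case, 1 February to 31 October 2021: 272 days; 272 / 30.4375 = 8.9 months.
- Narrowest case, 28 February to 1 October 2021: 215 days; 215 / 30.4375 = 7.1 months.
- The limit is two years, about 730 days. Since 272 < 730, it excludes nobody in either case.

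The schedule hardly alters this. Sleep is measured "the day before the application, the day the application ends, and the fourth day after the application". With three application days, the sequence runs from day 0 (pre-test) to day 7. If it must finish by 31 October, the last pre-test is on 24 October, which is 265 days or 8.7 months after 1 February.

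**2. Does the literal reading contradict the inclusion criterion?** No. Every child under 9 months post-transplant also satisfies a two-year maximum. The upper limit is redundant. The one-month minimum still operates: a child transplanted after about 1 October cannot reach 30 days by 31 October.

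**3. Does it contradict the start of data collection?** The earliest eligible child would be transplanted on 1 February and qualify on 1 March. February would then be empty: 28 of 273 calendar days, or 10.3%. The Protocol gives a period for collection and does not promise a child on its first day. An empty first month is awkward, but it does not contradict that period.

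**4. Is the Data Collection sentence a rival definition?** It says from whom data are collected. It omits the dates, but it also omits every inclusion criterion. A short restatement does not cancel what the population section and the criteria say.

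**5. Which reading does the context favour?** The other two uses of these months both denote the study period. An upper limit of two years serves a purpose only if transplants before February 2021 can qualify. If the dates mean hospitalisation or enrolment, eligible transplant dates run from about 1 February 2019 to 1 October 2021 (973 days, 32.0 months), the limit does its work and the tension disappears. On the literal reading they run from 1 February to 1 October 2021 (242 days, 8.0 months). The ratio 242 / 973 = 24.9% counts calendar dates, not children. The documents give no basis for converting it into patients.

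**6. Does the sample size depend on the answer?** The usual finite-population formula is n = N·k / (N − 1 + k), with k = 1.96²·p(1 − p) / d². The Protocol gives n = 50 and 95% confidence but not N, p or d. Solving for N gives N = 50(k − 1) / (k − 50). With p = 0.5 assumed:

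| d (assumed) | k | N implied by n = 50 |
|---|---|---|
| 0.03 | 1067.1 | 52 |
| 0.05 | 384.1 | 57 |
| 0.10 | 96.0 | 103 |

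The figure of 50 can be neither reproduced nor refuted under either reading. That gap is separate, and settling the dates would not close it.

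**7. Does any comparison depend on the answer?** Groups are drawn by lot within age strata, so both arms come from the same children whichever rule is used. Time since transplant is not among the control variables in Variables of the Study. The tests listed in Evaluation of Research Data, in the Protocol and in the SAP, do not refer to the date of transplant.

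**The case for a change.** The best argument for a change is that this sentence formally defines the population and that its grammar is not in doubt. Nowhere does the Protocol say that the dates mean hospitalisation or enrolment, so the reader has to override the sentence to reach the sensible meaning. The two readings differ by a factor of about four in transplant dates. One clarifying sentence would cost almost nothing. The record's release date, "Initial Release: 09/09/2021", is 220 days (7.2 months) after 1 February 2021, so a rule may already have been in use by then.

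Part of this stands. The wording is ambiguous, and the documents do not formally settle it. The rest carries less weight. Low cost is not a gain in itself: the sentence would record an intention that the context already indicates, and no estimate, test or stated figure would move. The release date does not show that anyone had been enrolled, and the Protocol writes of data collection mainly in the future tense. The range to which the result applies is better shown by the enrolled children's observed time since transplant than by a reworded sentence.

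**Conclusion.** No change to the plan follows. On the literal reading, time since transplant could not exceed about 7 to 9 months, depending on the days assumed, and the two-year limit would be redundant. It would not be contradicted. The likeliest explanation is a misplaced date phrase in a loosely worded text: the same months denote the study period in the other two places, and only that sense gives the two-year limit any purpose. This is an inference from context, since the documents do not state it.

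Under either reading the comparison between arms is sound in the children enrolled, and the stated 50 is equally uncheckable. The remaining effect is on describing the population. Analysts would ordinarily fill that gap by tabulating observed time since transplant, assuming that the form's time-of-transfer item is the transplant time.

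### Groups are assigned by papers drawn within age-stratified blocks with no concealment described, so the last assignments of a block could be foreseen: a conditional, minor risk of selection bias

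*Protocol*

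**What the plan says.** The Randomization section of the protocol states: "Assignment of the participants to the control and experimental groups will be done by stratification and block randomization method". There are four age strata (0-1, 2-5, 6-12 and 13-18 years). The groups are written on separate papers, and each child's group is "determined by drawing lots during data collection. In this way, the number of children included in the groups" is to be made equal. Lot-drawing is the only measure named against bias: "children who were stratified were assigned to the control and experimental groups by drawing lots". The Data Collection section repeats it without further detail: "Which group the participants will be in will be determined by drawing lots".

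Other parts of the protocol bear on the point:

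- Population and Sample of the Research gives 24 children per group, for therapeutic touch and for music.
- Sleep "will be evaluated with pre-test, post-test and follow-up applications". Under both group descriptions, the pre-test is recorded one day before the first session.
- Ethical Principles of Research puts consent before inclusion.
- Under Intervention Materials: "In order to practice therapeutic touch, the researcher attended a certified course organized by" a therapeutic touch association.
- Evaluation of Research Data, in the protocol and the SAP, lists multiple linear regression beside t-tests and ANOVA. It names no covariates and no primary test.
- Desing of Research says: "The research was planned as a quasi-experimental study".
- The front matter gives "Initial Release: 09/09/2021", and the study period is February to October 2021.

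Neither the protocol nor the available SAP text gives a block size, says who prepares, holds or draws the papers, mentions a sealed or opaque container, or places the draw before or after the pre-test. One section of the SAP was not available, so this absence holds only for the text that could be read.

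**The concern.** Drawing lots makes a sequence random. It does not hide what is left in a partly used block. The closest reading of blocking with equalised numbers is that a paper, once drawn, is not returned until the block is finished. That is a valid manual method, but the earlier draws then fix the last assignment of every complete block, and sometimes more than the last.

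If the person who chooses or schedules the next child can foresee the group, the choice or its timing can differ by group. A sleep difference could then partly reflect who was enrolled. Consent before inclusion does not close this gap, because foreknowledge can act on whom to approach. The setting is a single 19-bed clinic, and the researcher trained in therapeutic touch would plausibly know earlier assignments.

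**Working it through.** The plan gives no figure for predictability, so there is nothing to reproduce. The inputs from the protocol are two groups of 24 (48 children), four age strata, and significance at p<0.05. Assumed, because the documents do not give them: block size, stratum sizes, papers not returned within a block, a tracker who knows the block size and all past draws in the stratum, the size of steering, and two-sided testing.

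**Step 1: complete blocks.** In a 1:1 block of size 2h, an assignment is certain once one group's papers are exhausted. The expected number of certain assignments is 2h/(h+1) per block:

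- size 2: 2/2 = 1.00, or 50% of assignments
- size 4: 4/3 = 1.33, or 33%
- size 6: 6/4 = 1.50, or 25%

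**Step 2: unfinished blocks.** With 48 children over four strata, the last block of a stratum is often incomplete. The shares were simulated with random stratum sizes, under equal shares and under 10/30/40/20%:

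| Block size | Certain share | Of 48 | Best guess correct |
|---|---|---|---|
| 2 | 47.9% | 23 | 73.9% |
| 4 | 29.9% | 14 | 69.3% |
| 6 | 20.5-20.7% | 10 | 66.3% |

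Without blocking these would be 0% certain and 50% guessed correctly.

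**Step 3: effect on the test.** Suppose that a fraction f of the certain assignments is steered: children with prognosis higher by δ SD go to one group, and children lower by δ SD to the other. The false difference is 2 × δ × share × f. For an unadjusted t-test with 24 per group, the noncentrality is that difference × √(24/2) = difference × 3.46, on 46 degrees of freedom. For blocks of 4 (share 0.299):

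| δ | f | False difference | Error rate |
|---|---|---|---|
| any | 0 | 0 | 5.0% |
| 0.10 | 0.5 / 1 | 0.030 / 0.060 SD | 5.1% / 5.5% |
| 0.25 | 0.5 / 1 | 0.075 / 0.149 SD | 5.7% / 8.0% |
| 0.50 | 0.5 / 1 | 0.149 / 0.299 SD | 8.0% / 17.4% |

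**Step 4: opportunity.** 48 children in about 39 weeks is 48/39 = 1.2 per week. At equal shares over four bands that is about 0.3 per band per week, or one child every three weeks or so. Steering would usually need a deferral or a second candidate in the same band.

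**Step 5: children still to be allocated at the release date.** At even accrual from 1 February 2021:

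- study end 31 October: 48 × 52/273 = 9.1
- study end 1 October: 48 × 22/243 = 4.3

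**Step 6: would a new list help?** Mixed blocks of 4 and 6 used for all 48 children would cut certain assignments to about 6%, but that is no longer possible. Starting such a list for only the last 4 to 9 children leaves about 24-27% of the 48 certain. It raises the chance of a final gap of 4 or more between the groups from about 7-9% to about 22-30%, because part-used blocks are abandoned. Finishing the existing blocks avoids that cost.

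**The case against.** The strongest reply is that the harm rests on stacked assumptions. Block size, steering, who draws and who knows past draws are all absent from the documents. At the central assumption with half of the certain assignments steered, the error is 5.7%, close to nominal. The 8.0% and 17.4% require every foreseeable child to be steered, which accrual of about one child per band every three weeks makes unlikely. The error rates also use the least protective of the listed analyses, although the plan measures a pre-test and lists regression. Finally, recruitment was probably almost over at release. All of this stands, and it is why the point is minor and why no new allocation list is advised.

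It does not remove the gap. Concealment is still undescribed in the available text. The regression is listed without covariates, so the protection that it could give is not yet planned.

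Some stronger readings are tempting, and the documents do not support them:

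- **The allocation is biased or predictable in fact.** Nothing shows that anyone tracked the draws or acted on them.
- **The therapeutic touch practitioner enrols children or draws the lots.** The protocol says only that the researcher was trained to practise it.
- **The quasi-experimental label means that the trial is not randomised.** The Randomization section describes random allocation, and the procedure actually used decides how the study may be described.

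**Conclusion.** The concern holds as an open, conditional risk of selection bias of minor severity. If papers are used up within two-arm blocks and someone knows the block size and past draws, roughly 20% to 48% of the 48 assignments are foreseeable for blocks of 6 down to 2, and about 30% for blocks of 4. Without steering the bias is nil. With blocks of 4 and 0.25 SD steering, the error of an unadjusted t-test is about 5.7% to 8.0%, the upper figure being unlikely at this accrual.

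The two-arm reading rests on the 24/24 split and the Data Collection section. The Randomization section's wording of control and experimental groups does not match it and needs to be reconciled.

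**What to change.** 1. **All children.** Make the between-group analysis the regression already planned: sleep at post-test, and likewise at follow-up, on group, with the pre-test actigraphy value and age stratum as covariates, in place of an unadjusted independent t-test. This offsets steering on visible baseline sleep but not on unmeasured prognosis. It costs only wording, since the pre-test is already recorded.

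2. **Children not yet allocated.** Finish the existing blocks. Have a colleague who neither enrols nor treats put the remaining papers in sealed opaque envelopes, and open each only after consent and the pre-test recording. The planned day between pre-test and first session leaves room for this. Sealing does not stop someone deducing the last paper of a block, so also approach eligible children in order of eligibility and keep a dated log of those eligible, approached and enrolled. The cost is about an hour of preparation and a simple log, with no extra visits. The benefit reaches only about 4 to 9 children at assumed even accrual.

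3. **Reporting.** State the block size, who held and drew the papers, whether drawn papers were returned, and whether the draw came before or after the pre-test. Reconcile the quasi-experimental label and the control-group wording with the two-arm randomised allocation. This costs a few sentences and lets readers judge the risk for all children, including those already enrolled.

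### Two treated arms, an undefined control, and no statement of which test carries the conclusion: a within-arm or overall time effect could not be told apart from drift shared by both arms

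*Protocol*

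**What the plan says.** **Arms.** Data Collection in the protocol: "The study will consist of therapeutic touch group and music groups". It continues: "One of the experimental groups will be treated with therapeutic touch, and the other will be listened to a music". Procedures are written for these two groups only. Population and Sample of the Research: "Of the 50 patients sampled, 24 will be included in therapeutic touch groups and 24 in music concert groups".

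**Control.** Randomization: "Assignment of the participants to the control and experimental groups will be done by stratification and block randomization method". No control condition, and no number of children for one, appears in the supplied text.

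**Design and aim.** Design of Research: "The research was planned as a quasi-experimental study". Allocation is nonetheless by lot within age strata. Nursing Initiative gives the comparison of touch with music as the aim.

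**Outcome and visits.** Variables of the Study names actigraphy as the dependent variable without a sleep parameter. Sleep is measured three times: the day before the sessions, the day they end, and the fourth day after.

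**Tests.** Evaluation of Research Data, in both protocol and SAP, gives one list: independent t-test, dependent t-test and ANOVA, multiple regression and correlation, with significance at p<0.05. It names no primary contrast. Part of the SAP was not available, so statements of absence cover the supplied text only.

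**Dates.** The protocol is marked "Initial Release: 09/09/2021" and sets the research in the "Liver Institute Pediatrics Clinic between February 2021 and October 2021".

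**The concern.** A paired test asks whether sleep changed over time in children who were all treated. The answer combines any therapy effect with everything else that changes over the same days, such as getting used to the device, adapting to the ward, or recovery. Separating these needs a concurrent group without the therapy, and none is described. An overall time effect in a repeated-measures ANOVA has the same weakness.

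The comparison that randomisation protects is touch versus music. The plan has the data for it and states it as the aim, but the analysis text does not make it the test on which the conclusion rests. The title speaks of the effect of the two therapies on sleep. At stake is a report in which both arms improve at p<0.05 and this is read as evidence that the therapies work, although the design cannot show it.

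**Working it through.** **Inputs from the documents.** 24 per arm; three visits; significance at 0.05. The tests are taken as two-sided, which the plan does not state. Allocation: 24 + 24 = 48 of 50, leaving 2 children and no control group. The total of 50 cannot be reproduced, because the population size and margin of error are not given; nothing below depends on it.

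**Assumed.** No therapy effect, and the same drift in both arms. The documents give no actigraphy mean, SD or correlation, so drift d is shown as a range, in SD of the paired difference being tested.

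**1. Paired t-test within an arm.** The chance of a significant result in the direction of improvement is P(T > 2.069), where T is noncentral t with 23 df and noncentrality d × √24. For at least one of two independent arms it is 1 − (1 − p)².

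| d | noncentrality | given arm | at least one arm |
|---|---|---|---|
| 0 | 0 | 2.5% | 5% |
| 0.1 | 0.49 | 6.8% | 13% |
| 0.2 | 0.98 | 15% | 28% |
| 0.3 | 1.47 | 29% | 50% |
| 0.5 | 2.45 | 65% | 88% |

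These rates put all of d into the difference tested. If drift is instead linear across visits and defined at the last one, the pre/post difference carries d/2. At d = 0.5 this is 0.25, with noncentrality 1.22: about 22% in a given arm, and 1 − (1 − 0.216)² = about 39% in at least one.

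**2. Overall time effect, three visits, both arms in one model.** F test with 2 and 92 df, equal correlation between visits, drift defined at the last visit, direction ignored. With paired-difference SD = 1, noncentrality = 48 × Σ(m − mean)² / 0.5. At d = 0.5:

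- Plateau drift (0, 0.5, 0.5): 48 × 0.1667 / 0.5 = 16, significant in 95% of trials.
- Linear drift (0, 0.25, 0.5): 48 × 0.125 / 0.5 = 12, significant in 87%.

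Over d = 0 / 0.1 / 0.2 / 0.3 / 0.5, linear to plateau, the range is 5 / 9–10 / 21–27 / 43–55 / 87–95%.

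**3. Between-arm contrast.** Mean change is (drift + touch effect) in one arm and (drift + music effect) in the other. The difference is touch effect − music effect, so drift drops out. In simulation across these drifts, a single t-test on change rejected in 4.5–5.4% of null trials and group-by-time in 4.8–5.2%.

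**4. Several between-arm contrasts.** Drift still cancels in each one. Taking whichever of the two post-baseline visits is significant, for one parameter and with an assumed correlation of 0.5 between the two changes, gives about 9% instead of 5%, whatever the drift. That excess is multiplicity, a separate matter.

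**5. Power of the protected contrast.** Independent t-test, 24 per arm: 80% power at 0.83 SD of the analysed outcome, and 40% at 0.5 SD. Adjusting the post-test for baseline multiplies the detectable difference by √(1 − ρ²). For assumed pre/post correlations of 0.3, 0.5 and 0.7, 0.826 SD becomes 0.79, 0.72 and 0.59 raw SD (loss of one df ignored).

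**The case against.** The strongest reply is that the plan already states a comparative aim, lists the independent t-test first, and lists paired tests only as ordinary description of pre/post/follow-up data. The listed regression and control variables may point to an adjusted between-arm analysis, and ANOVA in dependent groups may be a translated description of a mixed design with a group-by-time term. Drift may also be small: a child must meet "Being within a period of at least one month and at most two years after the transplant" and be pain free, and measurement spans about a week. Control may be loose wording for one of the two treated groups.

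Much of this stands. The harm is conditional, the drift values are assumptions, and the control wording may need only an edit. But none of these intentions is written down, and without an untreated arm the trial cannot estimate the drift, small or not.

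Some stronger readings are tempting and not supported:

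- *That the sponsor will base its claim on pre/post tests.* No section says so.
- *That the quasi-experimental label leaves touch versus music unprotected too.* The arms run side by side and are drawn by lot, so common drift cancels.
- *That this protection is lost when several between-arm tests are run.* It is not; only the overall error rate rises.
- *That 65% and 88% are the pre/post error rates.* They apply only if the tested difference carries the full 0.5 SD.
- *That the release date shows the analysis was chosen after seeing data.* It falls within data collection, but does not show when the analysis was fixed or who had seen outcomes.

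**Conclusion.** The point holds in a limited form and should be fixed. As described, the design can compare touch with music; it cannot show that either improves sleep relative to no treatment. The supplied text does not say which test supports the conclusion, and it names a control that it does not define.

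The logical gap does not depend on the amount of drift. The error rates do: with no drift the paired test has its nominal rate, and they rise to 15% in a given arm at 0.2 SD and 65% at 0.5 SD, or to about 22% for pre/post if drift is linear and reaches 0.5 SD only at the last visit. Confidence is moderate, because part of the SAP could not be read and the harm arises only if a dependent test is used to support efficacy.

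**What to change.** 1. Reconcile the control wording under Randomization with the two-arm description: state that both arms are active comparators, or describe the control and its allocation.
2. If there are two arms, name one touch-versus-music contrast as the only test that supports an efficacy conclusion: one actigraphy parameter, at one visit, adjusted for the baseline value already collected. Label other parameters and visits secondary.
3. Report within-arm changes and any overall time effect descriptively, with confidence intervals and no efficacy claim.
4. State when the contrast was fixed relative to access to outcome data, since release (09/09/2021) falls within the February to October 2021 collection period. This discloses a late choice; it does not cure it.

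The cost is wording in both documents and a dated statement, with no extra patients if there are two arms. The trial gives up a claim against no treatment, which the described design cannot support anyway. What remains is a contrast with 80% power only for differences of about 0.83 SD, or somewhat smaller ones with baseline adjustment, so a non-significant result would not show that the two therapies are equivalent.
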